## 5. Study Design

### 5.1. Overall Design

Study GBGK is a Phase 4, single-center, randomized, cross-over, single-blind, placebo-controlled study to evaluate glucodynamic effects of dulaglutide after standardized test meal in Japanese patients with T2D.

The study includes a 10- to 28-day screening period, a 4-week treatment period (Period 1), a 4- to 6-week washout period, and a 4-week treatment period (Period 2).

[figure not shown]
Screening tests will be performed at Visit 1. After confirming eligibility, the patient will be randomized in a 1:1 ratio to dulaglutide 0.75 mg or placebo treatment in Period 1.

Meal tolerance test will be performed at baseline, 1, 2, and 4 weeks for each period. Time points for blood sampling will be 0, 30, 60, 90, 120, 180, and 240 minutes after the start of standardized test meal. Satiety will be also assessed at 0, 60, 120, 180, and 240 minutes after the start of standardized test meal. Detailed schedule of MTT is described in [Appendix 6](#). After completion of Period 1, all patients must have a 4- to 6-week washout period, and then will start Period 2 on the opposite treatment (patients taking dulaglutide will be switched to placebo and patients taking placebo will be switched to dulaglutide).

This is a single-blind study, and the treatment assignments will be blinded to patients until study completion.

Study governance considerations are described in detail in [Appendix 3](#).

[Figure GBGK.5.1](#) illustrates the study design.

▲ Meal tolerance test (240 minutes at 0, 1, 2, 4 weeks)

Abbreviations: CGM = continuous glucose monitoring; dula = dulaglutide; n = number of patients.

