#### **10.3.3. Pharmacodynamic Analyses**

##### **10.3.3.1. Pharmacodynamic Parameter Estimation**

Pharmacodynamic parameters will be calculated for glucose, insulin, glucagon, c-peptide, and triglyceride data following the standardized test meal at Weeks 0, 1, 2, and 4. The AUC(0-4h) will be calculated using the linear-trapezoidal method. This analysis will be performed for both original data and adjusted data with the predose value at each period. The parameters AUC(0-1h), AUC(0-2h), and AUC(0-3h) may also be calculated.

All PD parameters will be summarized and tabulated by treatment group and day. Summary statistics will be provided. The individual observed and mean time profile will be plotted by treatment group.

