## **Appendix 1. Abbreviations and Definitions**

---

Term	Definition
AE	adverse event: Any untoward medical occurrence in a patient or clinical investigation subject administered a pharmaceutical product that does not necessarily have a causal relationship with this treatment. An AE can therefore be any unfavorable and unintended sign (including an abnormal laboratory finding), symptom, or disease temporally associated with the use of a medicinal (investigational) product, whether or not related to the medicinal (investigational) product.
ALP	alkaline phosphatase
ALT	alanine aminotransferase
AST	aspartate aminotransferase
AUC(0-4h)	area under the concentration versus time curve from time zero to 4 hours
blinding	
A procedure in which one or more parties to the study are kept unaware of the treatment assignment(s). Unless otherwise specified, blinding will remain in effect until final database lock.
 
A single-blind study is one in which the investigator and/or his staff are aware of the treatment but the patient is not, or vice versa, or when the sponsor is aware of the treatment but the investigator and/his staff and the patient are not. A double-blind study is one in which neither the patient nor any of the investigator or sponsor staff who are involved in the treatment or clinical evaluation of the patients are aware of the treatment received

CGM	continuous glucose monitoring
CI	confidence interval
CIOMS	Council for International Organizations of Medical Sciences
complaint	A complaint is any written, electronic, or oral communication that alleges deficiencies related to the identity, quality, purity, durability, reliability, safety or effectiveness, or performance of a drug or drug delivery system.
compliance	Adherence to all the study-related requirements, good clinical practice (GCP) requirements, and the applicable regulatory requirements.
confirmation	A process used to confirm that laboratory test results meet the quality requirements defined by the laboratory generating the data and that Lilly is confident that results are accurate. Confirmation will either occur immediately after initial testing or will require that samples be held to be retested at some defined time point, depending on the steps required to obtain confirmed results.
CRF	case report form
CRP	clinical research physician
CT	computed tomography

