## Appendix 6. Meal Tolerance Test

Time	Procedure
-120 min	Physical exam, vital signs (sitting) Weight (only Day 1, Day 29, Day 57, and Day 85) ECG (only Day 1 and Day 57) Urine sampling for pregnancy test (only Day 1 and Day 57, if needed) Urinalysis and UACR (only Day 1, Day 29, Day 57, and Day 85) Blood sampling for hematology, clinical chemistry, endocrinology, HbA1c (only Day 1, Day 29, Day 57, and Day 85) Blood sampling for glucose, insulin, c-peptide, glucagon, and triglyceride (for 0 min) Satiety evaluation (VAS) (for 0 min)
0 min	Start standardized test meal a
30 min	Blood sampling for glucose, insulin, c-peptide, glucagon, and triglyceride
60 min	Blood sampling for glucose, insulin, c-peptide, glucagon, and triglyceride Satiety evaluation (VAS)
90 min	Blood sampling for glucose, insulin, c-peptide, glucagon, and triglyceride
120 min	Blood sampling for glucose, insulin, c-peptide, glucagon, and triglyceride Satiety evaluation (VAS)
180 min	Blood sampling for glucose, insulin, c-peptide, glucagon, and triglyceride Satiety evaluation (VAS)
240 min	Blood sampling for glucose, insulin, c-peptide, glucagon, and triglyceride Satiety evaluation (VAS)
After MTT	Dose of dulaglutide 0.75 mg or placebo (except Days 29 and 85)

Abbreviations: HbA1c = glycated hemoglobin; min = minutes; MTT = meal tolerance test; UACR = urine albumin/creatinine ratio; VAS = visual analog scale.

a Japanese standard test meal (480 kcal, carbohydrate: protein: fat = 2.8:1:1) should be ingested within 15 min.

---

**Appendix 7. Protocol Amendment H9X-JE-GBGK(a)  
Summary: A Phase 4 Study to Evaluate Glucodynamic  
Effects of Dulaglutide in Japanese Patients with Type 2  
Diabetes Mellitus**

---

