**Appendix 6:**

Time window before the meal tolerance test (MTT) is changed .

Minor editorial changes were made for accuracy, consistency and clarity.

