9.3 Pharmacodynamic Assessment

9.3.1 Pharmacodynamic Analysis

The baseline for all PD parameters is defined as the premeal value on Day 1 for the relevant period.

Primary Measure

The primary measure of PD is the change from baseline in glucose AUC(0-4h) at 4 weeks.

Secondary Measures

The following secondary measures of PD will be evaluated:

- The change from baseline in fasting blood glucose at 1, 2, and 4 weeks
- The change from baseline in postprandial blood glucose (30, 60, 90, 120, 180, and 240 minutes) at 1, 2, and 4 weeks
- The change from baseline in glucose AUC(0-4h) at 1 and 2 weeks
- The change from baseline in insulin (30, 60, 90, 120, 180, and 240 minutes) at 1, 2, and 4 weeks
- The change from baseline in insulin AUC(0-4h) at 1, 2, and 4 weeks
- The change from baseline in C-peptide (30, 60, 90, 120, 180, and 240 minutes) at 1, 2, and 4 weeks
- The change from baseline in C-peptide AUC(0-4h) at 1, 2, and 4 weeks
- The change from baseline in glucagon (30, 60, 90, 120, 180, and 240 minutes) at 1, 2, and 4 weeks
- The change from baseline in glucagon AUC(0-4h) at 1, 2, and 4 weeks
- The change from baseline in triglyceride (30, 60, 90, 120, 180, and 240 minutes) at 1, 2, and 4 weeks
- The change from baseline in triglyceride AUC(0-4h) at 1, 2, and 4 weeks

PD AUCs will be calculated for glucose, insulin, glucagon, c-peptide, and triglyceride data following the standardized test meal at Weeks 0, 1, 2, and 4. The AUC(0-4h) will be calculated using the linear-trapezoidal method and actual times. This analysis will be performed for both original data and adjusted data with the predose value at each period, i.e. incremental AUC (iAUC). The parameters AUC(0-1h), AUC(0-2h), and AUC(0-3h) will also be calculated for glucose, insulin, C-peptide, glucagon and triglyceride together with the corresponding iAUCs.

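### Does calculating AUC(0-4h) with actual sampling times pull premeal fasting time into the primary endpoint?

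*SAP*

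**What the plan says.** The primary endpoint is set in SAP 9.3.1: "The primary measure of PD is the change from baseline in glucose AUC(0-4h) at 4 weeks". The same section gives the calculation rule: "The AUC(0-4h) will be calculated using the linear-trapezoidal method and actual times". Protocol 10.3.3.1 has the trapezoidal rule without the reference to actual times: "The AUC(0-4h) will be calculated using the linear-trapezoidal method".

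On timing, Protocol 5.1 (repeated in SAP 5) reads: "Time points for blood sampling will be 0, 30, 60, 90, 120, 180, and 240 minutes after the start of standardized test meal". The procedure table in Protocol Appendix 6 has a row headed -120 min. It holds the physical examination and vital signs, on some days weight, ECG, urine and safety bloods, and the first test sample, entered as "Blood sampling for glucose, insulin, c-peptide, glucagon, and triglyceride (for 0 min" with the bracket then closed. The next row, 0 min, contains one item: "Start standardized test meal".

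Protocol Appendix 1 defines the parameter as "area under the concentration versus time curve from time zero to 4 hours". SAP 4.1 keeps the same limits of 0 to 4 hours in the primary objective.

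**The concern.** The sample that opens the curve is nominally at 0 min but is drawn before the meal, at a lead that is not fixed within the 120 minutes. The SAP asks for actual times and states no exception. A program that took the recorded clock times at face value would start the first trapezoid at the premeal draw and end the last one whenever the 240 min sample was taken. Areas would then cover different durations at different visits.

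The stake would be the primary endpoint. Two extra hours at fasting glucose levels can exceed the planned treatment difference of 190 mg*hr/dL, and a lead that varied between visits would add noise in a study sized for 11 completers. The same rule also governs AUC(0-1h), AUC(0-2h), AUC(0-3h) and the incremental areas for five analytes.

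**Working it through.** **Inputs from the documents.** Difference 190 mg*hr/dL, SD 140, intra-patient correlation 0.3, 11 completers, one-sided 0.025, power 93% (Protocol 10.1, SAP 7). Fasting glucose at entry 120 to 200 mg/dL (Protocol 6.1, criterion 4).

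**Assumed, because the documents do not give them.** Premeal glucose G0 = 150 and 30 min glucose G30 = 200 mg/dL unless stated otherwise; lead time L in minutes.

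**1. The plan's own figure.** SD of the within-patient difference = 140 × √(2 × (1 − 0.3)) = 165.7. Noncentrality = 190 × √11 / 165.7 = 3.80. Noncentral t power is 92.8% with 10 df and 92.2% with 9 df, which agrees with 93%.

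**2. Literal reading, area starting at the draw.** Extra area = (L/60) × (G0 + G30)/2.
- L = 30: 0.5 × 175 = 87.5
- L = 60: 1 × 175 = 175
- L = 120: 2 × 175 = 350

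With glucose flat at 120 to 200 mg/dL, L = 120 gives 240 to 400 mg*hr/dL.

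**3. Readings that keep the limits of 0 and 4 hours.**
- Premeal sample placed at time 0: extra area 0.
- Value at time 0 interpolated between the draw and the 30 min sample: G(0) = G0 + (G30 − G0) × L/(L + 30), and the area shifts by 0.5 × (G(0) − G0)/2. For L = 30, 60 and 120, G(0) is 175, 183.3 and 190, so the shift is 6.3, 8.3 and 10 mg*hr/dL.
- With G0 = 160 and L = 120, G30 = 200 gives a shift of 8 and G30 = 220 gives 12. If those were the two treatments, the contrast would move by 12 − 8 = 4 mg*hr/dL, or 4/190 = 2% of the planned difference.

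**4. Noise under the literal reading.** If L were uniform over 0 to W minutes, the added SD per AUC would be e = (W/60)/√12 × 175, the mean height of the first trapezoid. The SD of the difference becomes √(165.65² + 2e²) if only Week 4 is affected, and √(165.65² + 4e²) if the Week 0 AUC is fully affected as well. Power is with 9 df.

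| W (min) | e | Week 4 only | Week 4 and Week 0 |
|---|---|---|---|
| 30 | 25 | 91% | 90% |
| 60 | 51 | 87% | 82% |
| 120 | 101 | 73% | 58% |

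The large losses need both the literal reading and a lead spread over the full two hours.

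**5. A lead that differs by week.** Appendix 6 gives Days 1 and 57 the same premeal procedures, and likewise Days 29 and 85. The primary contrast compares the treatments within Week 4, so a lead tied to the visit type applies to both. What would remain is L/60 times any treatment difference in the early glucose values: for an assumed 10 to 30 mg/dL at L = 120, that is 20 to 60 mg*hr/dL. This would be real drug effect outside the defined window, and it does not arise under step 3.

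**6. The last sample.** A 240 min draw taken 10 minutes late adds 10/60 × 150 = 25 mg*hr/dL if the area is not cut at 4 hours. A random error with SD 5 minutes (assumed) adds 5/60 × 150 = 12.5, and the SD of the difference goes from 165.7 to √(165.65² + 2 × 12.5²) = 166.6.

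**The case for a change.** The strongest case for acting is that the instruction is unqualified. Placing a premeal draw at time 0 is not, strictly, using its actual time. The SAP says in its introduction that it supersedes the protocol's statistical considerations, so the protocol's silence on times cannot be relied on. Three implementations are open: start at the draw, assign time 0, or interpolate. No text says how the 4 hour limit is reached when the last sample is early or late. The study is blinded only to patients, which favours settling such choices before data are seen, and doing so would take one sentence.

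Part of this stands. The SAP does not state how the premeal time or an off-schedule final sample is handled. But superseding the protocol does not remove the limits, because the SAP carries 0 to 4 hours in its own primary objective and lists the first sample as the 0 minute point in its own design section. Of the three implementations, the first yields something other than the named parameter, and the other two differ by a few mg*hr/dL. Variation in lead between visits is possible but not documented. The amendment overview describes the block as a window ("Time window before the meal tolerance test (MTT) is changed"), and no actual draw times are reported. Extra procedures on some days do not show that the test sample was drawn earlier on those days.

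**Conclusion.** No change to the plan follows. The wording leaves a derivation detail unstated, but the definition of the parameter, the choice of meal start as time zero and the label on the draw all point to treating the premeal sample as the value at time 0, with actual times for the samples after the meal. On that reading the error is zero. Interpolation to time 0 shifts each AUC by about 6 to 12 mg*hr/dL, against a planned difference of 190, and the treatment contrast by less. Ordinary timing error in the last sample changes the SD of the difference by about 1 mg*hr/dL.

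The figures of 240 to 400 mg*hr/dL and the falls in power hold only if the area is begun before the meal, contrary to its definition, and the falls also need lead times that vary widely at random. The conclusion rests on the analyst respecting the stated limits. The glucose values and timing errors used here are assumptions, because the documents give neither.

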9.3.2 Pharmacodynamic Statistical Methodology

All PD parameters will be listed and summarized by treatment group and week. Individual observed and changes from baseline in glucose, insulin, glucagon, C-peptide, and triglyceride concentrations will be listed and summarized and their mean time profiles will be plotted by treatment group together with changes from baseline.

PD AUCs and iAUCs on Weeks 0, 1, 2, and 4 will be analyzed using a mixed-effects linear model for glucose, insulin, glucagon, C-peptide, and triglyceride . The model will include

treatment, sequence, period, week and treatment-by-week interaction as fixed effects, baseline as a covariate and patient as random effect.

The least squares means and the 95% CIs by treatment group will be tabulated and plotted. Comparisons between dulaglutide and placebo will be performed. Difference of least squares means of dulaglutide to placebo, and the 95% CIs, will be tabulated. Example SAS code is given below:

```
proc mixed data=pd;
class patient treatment sequence period week;
model pd = baseline treatment sequence period week treatment*week / ddfm=kr;
repeated week(treatment) / subject=patient type=un;
lsmeans treatment*week / pdiff alpha=0.05;
run;
```

The repeated patient effect models the within-patient errors using an unstructured variance-covariance matrix. If the analysis fails to converge, the following variance-covariance matrix will be used (in order) until one converges:

1. compound symmetry,
2. banded, and then
3. first-order autoregressive.

Continuous plasma glucose monitoring (CGM)

For the CGM data, parameters will be derived from the raw data collected through Day -1 to Day 6 (7 days), of CGM device use by patient and treatment.

The following notation will be used in the definition:

- n represents the number of time points within a day
- i represents a time point within a day
- m represents a day

Within-day glucose SD:

$$SD_m = \sqrt{\frac{\sum_{i=1}^n (BG_i - \left\{ \frac{\sum_{i=1}^n BG_i}{n} \right\})^2}{n-1}}$$

Mean amplitude of glycemic excursions (MAGE):

this parameter is calculated based on the arithmetic mean of differences between consecutive peaks and nadirs of differences greater than one SD of mean glycemia. Mean of the differences between consecutive peaks and nadirs in BG that meet qualifying criteria

$$MAGE_m = \frac{\sum_{l=1}^p |BG_l - BG_{l-h}|}{p}$$

where,

x_l = the low point in consecutive BG time points for the M^{th} day (nadir)

x_{l-h} = the high point in consecutive BG time points for the M^{th} day (peak)

p = the number of qualifying differences: $(BG_l - BG_{l-h}) \geq 1 \text{ SD}(\text{daily BG values})$ and that follow the direction of the first qualifying difference within the BG time points for the M^{th} day

Daily average, daily standard deviation, and daily MAGE from glucose data will be summarized. Individual (by patient) and mean by treatment of glucose data will be plotted over the days.

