  - B. Either one highly effective method of contraception (such as combination oral contraceptives, implanted contraceptives, or intrauterine device) or a combination of two effective methods of contraception (such as male or female condoms with spermicide, diaphragms with spermicide, or cervical sponges) will be used. The patient may choose to use a double barrier method of contraception. Barrier protection methods without concomitant use of a spermicide are not a reliable or acceptable method. Thus, each barrier method must include use of a spermicide. It should be noted that the use of male and female condoms as a double barrier method is not considered acceptable due to the high failure rate when these methods are combined.
- 3) Women not of childbearing potential may participate and include those who are:
  - A. infertile due to surgical sterilization (hysterectomy, bilateral oophorectomy, or tubal ligation) or congenital anomaly such as mullerian agenesis; or
  - B. postmenopausal – defined as either
    - i. A woman at least 50 years of age with an intact uterus, not on hormone therapy, who has had either
      - a) cessation of menses for at least 1 year, or
      - b) at least 6 months of spontaneous amenorrhea with a follicle-stimulating hormone  $>40$  mIU/mL; or
    - ii. A woman 55 years or older not on hormone therapy, who has had at least 6 months of spontaneous amenorrhea; or
    - iii. A woman at least 55 years of age with a diagnosis of menopause prior to starting hormone replacement therapy.
- [2] have T2D (based on the World Health Organization's [WHO] diagnostic criteria) for at least 1 year.
- [3] have diet and exercise therapy only (no oral antihyperglycemic medication for at least 3 months prior to Visit 1).
- [4] have a fasting blood glucose value of  $\geq 120$  and  $\leq 200$  mg/dL at Visit 1.
- [5] have a screening body weight of  $\geq 50$  and  $\leq 80$  kg.

- [6] are reliable and willing to make themselves available for the duration of the study and are willing to follow study procedures.
- [7] are able and willing to give signed informed consent.

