7. SAMPLE SIZE JUSTIFICATION

Up to 14 patients may be entered to randomize 12 patients and complete at least 11 patients. Patients will be randomized in a 1:1 ratio to one of two sequences. Assuming one dropout, the sample size of 11 patients would provide 93% power to demonstrate superiority of dulaglutide to placebo. This computation assumes the true treatment difference in glucose AUC(0-4h) is 190 mg*hr/dL, a common standard deviation of 140 mg*hr/dL, intra-patient correlation of 0.3, and a one-sided significance level of 0.025.

Patients who are randomized but do not complete study treatment may be replaced at the discretion of the investigator and Lilly clinical pharmacologist.

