9. STATISTICAL METHODOLOGY

9.1 General

Data listings will be provided for all data that is databased. Summary statistics and statistical analysis will only be presented for data where detailed in this SAP. For continuous data, summary statistics will include the arithmetic mean, arithmetic standard deviation (SD), median, min, max and N; for log-normal data the geometric mean and geometric coefficient of variation (CV%) will also be presented. For categorical data, frequency count and percentages will be presented. Data listings will be provided for all patients up to the point of withdrawal, with any patients excluded from the relevant population highlighted. Summary statistics and statistical analyses will generally only be performed for patients included in the relevant analysis population. For the calculation of summary statistics and statistical analysis, unrounded data will be used.

Mean change from baseline is the mean of all individual patients’ change from baseline values. Each individual change from baseline will be calculated by subtracting the individual patient’s baseline value from the value at the timepoint. The individual patient’s change from baseline values will be used to calculate the mean change from baseline using a SAS procedure such as Proc Univariate.

Data analysis will be performed using SAS® Version 9.3 or greater.

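### The primary mixed model puts pre-dose Week 0 in the response beside an undefined AUC baseline; with a Day 1 AUC baseline the unstructured fit has no maximum, and the first fallback understates the Week 4 standard error

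*SAP*

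**What the plan says.** SAP 9.3.1 names the primary endpoint: "The primary measure of PD is the change from baseline in glucose AUC(0-4h) at 4 weeks". The same section fixes the baseline: "The baseline for all PD parameters is defined as the premeal value on Day 1 for the relevant period". SAP 9.1 forms each change by subtracting the patient's "baseline value from the value at the timepoint".

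SAP 9.3.2 then gives the model: "PD AUCs and iAUCs on Weeks 0, 1, 2, and 4 will be analyzed using a mixed-effects linear model". Fixed effects are treatment, sequence, period, week and treatment-by-week, with one baseline slope for all weeks. The example code has the covariance line `repeated week(treatment) / subject=patient type=un`, an 8×8 unstructured matrix per patient (4 weeks × 2 treatments, 36 parameters), with Kenward-Roger degrees of freedom. On failure: "If the analysis fails to converge, the following variance-covariance matrix will be used (in order) until one converges". The list is compound symmetry, banded, then first-order autoregressive.

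Protocol 10.3.3.2 also models Week 0, but calls the baseline the predose rather than the premeal value. The Schedule of Activities (footnote h) and Protocol Appendix 6 place dosing after the meal test. SAP 11 reports no changes from the protocol.

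**The concern.** Three linked problems.

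1. **The AUC baseline is not defined.** A premeal glucose is in mg/dL (Protocol 6.1, criterion [4]: "have a fasting blood glucose value of" 120 to 200 mg/dL). The AUC is in mg*hr/dL (SAP 7). One cannot be subtracted from the other, so a change in AUC needs the Day 1 AUC. Because dosing follows the meal test, the protocol's predose wording allows that reading. Two programmers could follow the SAP and fit different primary models.

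2. **Week 0 is a pre-treatment outcome.** With the Day 1 AUC as covariate, the Week 0 response is its own covariate. With change as the response, Week 0 is zero for everyone. Either way those rows can be fitted exactly.

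3. **The first fallback does not match the contrast.** In each patient, Week 4 on dulaglutide and Week 4 on placebo lie in different periods. Patient-level compound symmetry gives that pair the same correlation as two visits in one period.

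At stake are the width of the primary 95% CI and the error rate of the superiority test.

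**Working it through.** **Planned power (reproduced).** Inputs from SAP 7: difference 190, SD 140, "intra-patient correlation of 0.3", 11 completers, one-sided 0.025.
- SE = 140 × √(2 × (1 − 0.3) / 11) = 49.9; noncentrality = 190 / 49.9 = 3.80.
- Noncentral t power is 92.8% with 10 df, against the stated 93%, and 91.3% with 8 df.

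The sample size therefore already assumes a between-period paired contrast at Week 4.

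**Unbounded likelihood (Day 1 AUC baseline, n = 11).** There are 11 × 2 = 22 Week 0 rows. Slope 1, with sequence, period and Week 0 treatment effects of 0, fits all of them exactly. Five mean parameters are tied down by those rows (intercept, slope, sequence, period, treatment at Week 0). Each 100-fold cut in the Week 0 variance should then raise the REML log-likelihood by (22 − 5)/2 × ln(100) = 39.1.
- Computed on one simulated data set: −393.3, −352.5, −313.3, −274.1, −235.0. The rise per step settles at about 39 and the slope goes to 1.000.
- A change-score response gives the same values.
- With a simulated fasting-type baseline, the likelihood falls along this path, so the degeneracy is absent.

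**Fallback: patient-level compound symmetry, Week 0 kept, Day 1 AUC baseline, no treatment effect.** SD 140 and between-period r 0.3 come from the plan. Within-period r is not in the documents and is assumed. Error rates come from 3,000 runs per setting (Satterthwaite df; Monte Carlo SE 0.4 to 0.7 points). The SE columns come from a separately coded run, n = 11.

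| Within-period r | Error, n = 11 | Error, n = 12 | Mean SE | True SD | Ratio |
|---|---|---|---|---|---|
| 0.3 | 7.3% | 6.9% | 49.9 | 54.2 | 0.92 |
| 0.5 | 8.9% | 9.3% | 43.7 | 50.4 | 0.87 |
| 0.7 | 10.4% | 10.2% | 35.0 | 42.3 | 0.83 |
| 0.85 | 10.5% | 11.7% | 25.3 | 31.5 | 0.80 |

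If the 1-week correlation decays towards 0.3, error is 9.1%, 13.3% and 18.2% (n = 11) and 9.4%, 14.1% and 17.0% (n = 12) for 1-week r of 0.5, 0.7 and 0.85. At n = 11 and r 0.7 with decay, the mean SE is 42.1 against a true SD of 56.0, a ratio of 0.75.

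**Degrees of freedom.** The compound-symmetry contrast uses about 69. A Week 4 analysis of within-patient differences with intercept, sequence and baseline difference has 11 − 3 = 8. At r 0.7 the 95% half-width is 35.0 × 1.995 = 70 under compound symmetry. A Week-4-only model with SE 42.6 gives 42.6 × 2.306 = 98.

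**Alternatives, same null settings.**
- Compound symmetry with a premeal covariate (assumed r 0.8 with the same-day AUC): 6.0% to 14.4%.
- Week 0 dropped, compound symmetry kept: 5.3% to 14.4%.
- Random patient plus random patient-by-period (n = 11, 1,500 runs): 4.5% to 5.7% if exchangeable; 5.1%, 8.5% and 10.5% with decay.
- Week 4 two-period ANCOVA: 4.3% to 5.3% in all settings.

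**The case against.** The harm needs a chain of events: the baseline is read as the Day 1 AUC (or the fit fails for another reason), the software reports non-convergence, and the analyst moves to compound symmetry. SAP 9.3.1 literally says premeal, and with that covariate the unstructured fit usually converges with no inflation shown. SAS was not run, so the switch to the fallback is inferred from the unbounded likelihood. The simulations used Satterthwaite or residual df, not Kenward-Roger. The TFL shells, which are not available here, might show the baseline used.

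The plan also gives only one correlation. Taking 0.3 both within and between periods, the error is about 7%; larger figures rest on assumed values, and 18.2% is the extreme corner. At the planned difference, 190 / 42.3 = 4.5, with power of about 97% on 8 df, so the superiority decision would rarely change. The main harm would be a CI that is too narrow.

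All of this stands as a limit on size and likelihood. It does not rescue the text. The premeal reading avoids the degeneracy only by leaving the primary change in AUC without a usable baseline, and the unboundedness under the other reading is exact algebra, independent of any assumed value.

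**Conclusion.** The point holds and should be fixed. The AUC baseline is undefined as written. Under the reading that the primary endpoint requires, Week 0 in the response makes the unstructured fit unbounded. If compound symmetry is then used, the Week 4 SE is understated by 8% to 20% under exchangeable within-period correlation of 0.3 to 0.85, and by 25% in the decay case at r 0.7. Two-sided error is about 7% at the plan's own correlation, 7% to 12% over the exchangeable range, and 9% to 18% with decay.

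These sizes are conditional on the fallback being reached, on complete data, and on within-period correlations that the documents do not give. Confidence is moderate. The planned power figure is not in error.

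**What to change.** 1. State that the baseline is the Day 1 value of the same parameter in the same period: the Week 0 AUC for an AUC, the Week 0 iAUC for an iAUC.
2. Keep only Weeks 1, 2 and 4 in the response. Alone this is a partial cure, because patient-level compound symmetry still mis-sizes the between-period contrast.
3. For the primary Week 4 contrast, prespecify a two-period ANCOVA on within-patient differences, with sequence and the Day 1 difference as covariate.
4. For the longitudinal model, use `random intercept / subject=patient; repeated week / subject=patient*period type=un` (3×3). A small check (n = 11, 600 to 800 runs, 15 to 18 df assumed, unadjusted SE) gave about 5% to 6% error in most settings but about 8% under decay at r 0.85. It is reasonable, but less secure than the ANCOVA for the primary contrast.
5. Replace the fallback list with structures that separate within-period from between-period correlation, ending in the ANCOVA.
6. Record the changes in SAP 11.

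The cost is SAP wording and a few lines of code, before the sign-off that SAP 3 requires ahead of first dosing. The ANCOVA uses only patients with Week 4 data in both periods. The SE will be larger than under compound symmetry (about 42 instead of 35 at n = 11, r 0.7), but still below the 49.9 behind the planned power.

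### SAP 9.3.2 contradicts itself on MAGE: with its own nadir and peak labels the signed 1-SD condition can never be met, although an unsigned threshold was plainly intended

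*SAP*

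**What the plan says.** The CGM part of SAP 9.3.2 defines MAGE in four pieces.

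- **Prose.** MAGE is the "arithmetic mean of differences between consecutive peaks and nadirs of differences greater than one SD of mean glycemia". No sign is attached to these differences.
- **Formula.** The numerator sums `|BG_l - BG_{l-h}|`, with absolute bars, for l = 1 to p. The divisor is p.
- **Labels.** Index l is "the low point in consecutive BG time points" of the day (the nadir). Index l-h is "the high point in consecutive BG time points" of the day (the peak). The labels are attached to x, whereas the formula uses BG.
- **Count.** The SAP sets "p = the number of qualifying differences". A difference qualifies if `(BG_l - BG_{l-h}) >= 1 SD` of the daily values, without absolute bars, and if it runs in the same direction as the day's first qualifying difference.

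The same section defines the within-day SD, SD_m, over all n time points of the day with divisor n-1. MAGE is then summarized with the daily average and daily SD. Protocol 10.3.4 names MAGE but gives no formula, and SAP section 3 says the SAP supersedes the protocol's statistical text. SAP 9.3.2 is therefore the only definition.

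**The concern.** The count line decides which excursions enter MAGE, and as printed it admits none. That contradicts the prose and the numerator a few lines away.

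The labels raise a second, separate difficulty. If l-h is the earlier point and l the later one, the labels allow only falls from a peak to a nadir, and the first-direction rule has nothing to decide. If that rule is meant to operate, the labels are the wrong way round on any day whose first qualifying swing is a rise.

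Two programmers could therefore derive different MAGE values from the same CGM trace and both cite the SAP. MAGE and daily SD are the only planned CGM summaries that measure variability within a day, which is the subject of the exploratory objective.

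**Working it through.** The documents state no MAGE value, so there is no figure of the plan's to reproduce.

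**1. The printed condition.** A nadir is no higher than its adjoining peak, so `BG_l - BG_{l-h} <= 0`. On any day with varying glucose SD_m > 0. The requirement `BG_l - BG_{l-h} >= SD_m` therefore cannot hold. Hence p = 0, the sum is empty and MAGE = 0/0.

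**2. Seven-point illustration.** The values are assumed, because the documents contain no CGM data. Turning points in time order: 120, 210, 130, 190, 110, 230, 140 mg/dL.

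- Mean = 1130/7 = 161.4. Sum of squared deviations = 13,685.7. SD = sqrt(13,685.7/6) = 47.8.
- Nadir minus preceding peak: 130-210 = -80; 110-190 = -80; 140-230 = -90. None is at least +47.8, so p = 0 as printed. All three exceed 47.8 in size.

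**3. The same day with an absolute threshold.** Rises are 90, 60 and 120; falls are 80, 80 and 90. All six exceed 47.8.

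| Reading | Calculation | MAGE (mg/dL) |
|---|---|---|
| Direction of first qualifying difference (here a rise) | (90+60+120)/3 | 90.0 |
| Falls only (labels read as time order) | (80+80+90)/3 | 83.3 |
| Both directions | 520/6 | 86.7 |

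The two readings at issue differ by 90.0 - 83.3 = 6.7 mg/dL.

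**4. Limit of the illustration.** The 47.8 comes from seven turning points, whereas SD_m uses every reading of the day. The values in the table stand for any SD_m up to 60. If SD_m lay above 60 and up to 80, the rise of 60 would drop out: the first-direction value would be (90+120)/2 = 105 and falls-only would stay at 83.3.

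**5. Check with SD over all readings.** 2,000 synthetic days were generated from assumed three-meal profiles sampled every 15 minutes, with reversals smaller than 1 SD collapsed. No day had a qualifying difference under the printed condition. With the absolute threshold, mean MAGE was 84.9 under the first-direction rule, 75.6 for falls only and 80.2 for both. First-direction and falls-only values differed by more than 10% on 67% of days. In these profiles the first qualifying swing was always a rise, so the size of the gap depends on the assumptions. That the printed condition is never met does not.

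**The case against.** The strongest reply is that this is a sign slip which no competent programmer would follow. The prose is unsigned and the numerator has absolute bars. The first-direction rule makes sense only if rises and falls can both qualify, so it presupposes a threshold on size. These cues agree, and the reply largely stands: the intended threshold and direction rule can be read from the section.

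A second reply is that nadir and peak may be mere labels for the low and high points, with no time order implied. Under absolute bars there is then no conflict with the direction rule. That reading is possible, but the notation does not settle it: l-h looks like an earlier position, and l also serves as the summation counter.

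Third, the bars in the count line may have been lost when the PDF was converted to text. Those in the numerator survived, so the text cannot decide this. The labelling difficulty remains either way.

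A reader might also infer more than the documents support:

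- **That numerator and divisor use different sets of differences.** The sum runs to p and p counts the qualifying differences, so they share one set.
- **That the programmer would choose a rule knowing the treatment.** Protocol 7.3 describes a patient-blind study and refers to a separate Blinding Plan. The documents do not say what the programmer knows.
- **That greater than in the prose against at-least in the condition matters.** It does so only if a difference exactly equals that day's SD.

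**Conclusion.** The point holds as an internal contradiction in SAP 9.3.2. The printed condition can never be met under the SAP's own labels; this follows from algebra and needs no data. It would be too strong to say that MAGE cannot be computed from the SAP at all, because the rest of the definition shows an unsigned 1-SD threshold.

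The direction question is an ambiguity that does not prevent computation but can change the value: 90.0 against 83.3 mg/dL in the illustration. Those figures rest on assumed turning points and an SD taken from them alone, so they show that the readings differ and do not predict by how much in this trial.

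The importance is low. MAGE is summarized descriptively, with no test or interval planned. The protocol's listed endpoint for the exploratory objective is the time course of daily average glucose by CGM. The listed endpoints, the primary analysis and the power calculation are unaffected.

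**What to change.** In SAP 9.3.2, before the CGM derivations are programmed:

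1. Define l and l-h as consecutive turning points (a peak and a nadir in either order) in time order, and use one symbol, BG, throughout.
2. Write the condition as `|BG_l - BG_{l-h}| >= 1 SD_m`, where SD_m is the within-day SD over all time points already defined in that section. Align the prose with it.
3. Keep the first-qualifying-direction rule and state that it applies to both the sum and the count p.
4. State that MAGE is missing for a day with p = 0. SAP 13.2 covers only how missing data appear in listings.

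The cost is about two lines of SAP text, with no change to data collection or study conduct.
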